15.3 OPERATIONAL DEFINITION - SERIOUS ADVERSE EVENTS/REACTIONS (SAEs/SARs)

It is acknowledged that this patient group are likely to experience numerous adverse events related to co-morbidities other than PMR or its treatment. In acknowledgement of this and the well-known safety profile of DMARDs, in this study only serious adverse events that are suspected to be related to PMR or the IMPs will be reported.

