6.3 SECONDARY OBJECTIVES

Secondary objectives are:

- to assess the impacts over 18 months of adding DMARD to steroids, by comparing treatment groups for:
 - PMR symptom severity (PMR-IS and sub-domains)
 - Health-related quality of life (EQ-5D-5L)
 - PMR Disease Activity (PMR-AS)
 - time to steroid cessation
 - steroid-free remission at 18 months
 - time to PMR relapse and number of PMR relapses
 - cumulative (prednisolone equivalent) steroid dose prescribed

- Safety:
 - adverse events of special interest related to investigational medicinal products or PMR
 - serious adverse events and SUSARs
 - glucocorticoid toxicity
 - diagnosis of adrenal insufficiency
 - time to diagnosis of GCA
- to estimate cost-effectiveness over 18 months post randomisation via a within-trial analysis and the long-term impact of the treatment options using a decision analytical model.
- to estimate the impact of adoption of the intervention on rheumatology service capacity

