15.2 OPERATIONAL DEFINITION & REPORTING ADVERSE EVENTS/REACTIONS (AES/ARS)

Information about adverse events/reactions whether volunteered by the participant, discovered by investigator questioning or detected through physical examination, laboratory test or other investigation will be collected and recorded on the relevant Clinical Assessment CRF. All adverse events should be recorded in the participant's medical notes so that they can be followed up if necessary.

This is a randomised controlled trial using treatments with well-known safety profiles already established in the therapy of rheumatological conditions. Although not licensed for PMR, MTX has been shown in clinical practice to be safe and well-tolerated in a PMR population (31). Similarly, in the previous trial by Caporali et al., the main adverse effects that occurred more often in the MTX than placebo arm of the trial was mild gastrointestinal adverse effects. The strategy being tested is DMARD (MTX or LEF) in conjunction with usual care steroid taper, compared to usual care steroid taper alone. The IMPs are defined as the DMARDs, MTX or LEF.

Therefore, the following expected adverse events, related to either tapering of steroid for PMR or to the IMPs, will be reported. It is noted that causality (determination that an Adverse Event is an Adverse Reaction related to a particular IMP) may be difficult to determine since participants will also be receiving other medications, including steroids which should not be stopped abruptly and which can cause many of the adverse events listed below; however, because MTX is administered weekly, assessment of causality may be facilitated by temporality of symptoms in relation to MTX administration

15.2.1 Expected AEs potentially related to tapering of steroid for PMR:

- Diagnosis of adrenal insufficiency – see section 17.2.2
- Diagnosis of giant cell arteritis

15.2.2 Expected AEs/ARs potentially related to MTX:

Please report the following if severity is consistent with **CTCAE grade 2 and above (see Appendix 3)**:

- Clinically significant deranged liver function test values (as judged by the local investigator)
- Clinically significant cytopenia (as judged by the local investigator)
- Depression (diagnosis of depression, or initiation or increase of depression medication)
- Infection (infection requiring treatment with oral, IV or IM antibiotics, or any episode of shingles, or a positive community test for COVID-19)

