15.4 RECORDING AND REPORTING AEs, ARs, SAEs, SARs AND SUSARs

Monitoring for safety events should commence on the date of consent and continue until a minimum of 30 days post last dose of randomised treatment.

AEs and SAEs will be collected on the relevant eCRF and reported to CTRU from the date of consent and continue until a minimum of 30 days post last dose of randomised treatment.

Reporting of ARs, SARs and SUSARs to CTRU should commence on the date of the first IMP dose taken and continue until a minimum of 30 days post last dose of randomised treatment.

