** The following events should also be regarded as SAEs in participants receiving **abatacept**:
1) Cancer 2) Overdose leading to an SAE 3) Pregnancy 4) Medication error leading to an SAE 5) Suspected transmission of an infectious agent via the drug 6) Potential Drug Induced Liver Injury (DILI).

*The Chief Investigator (or delegate) will review all received SUSARs for seriousness, expectedness and causality. All SUSARs or increase in trends or severity of SARs will be identified and expeditiously reported to the MREC, MHRA and Sponsor.

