As for the primary outcome, if any steroid medications other than prednisolone are prescribed, these will be converted to an agreed “prednisolone equivalent dose” prior to analysis.

Safety

Adverse events (AEs) of Special Interest reported over 18 months post randomisation will include those relevant to PMR and/or investigational medicinal product.

Serious adverse events (SAEs) and SUSARs regardless of relationship to PMR or investigational product reported over 18 months post randomisation.

Glucocorticoid toxicity

Glucocorticoid toxicity is defined as per the OMERACT Glucocorticoid Core Domain Set (infection, diabetes, hypertension, fracture) adapting measures from the Glucocorticoid Toxicity Index (67)

Time to development of GCA

Time to development of GCA (defined as rheumatologist-confirmed and treated according to GCA treatment protocols specified in 2020 BSR guideline, without the diagnosis later being revised from GCA during the 18 month period) will be defined as the duration between randomisation and date of GCA diagnosis. Participants who are not diagnosed with GCA during follow-up will be censored at 18 month, or else at date of death or withdrawal.

Proportion of participants diagnosed with adrenal insufficiency

The proportion of participants who are identified as diagnosed with adrenal insufficiency will be the proportion of participants who either have a low value of 9am cortisol test, or an intermediate value followed by a positive short synacthen test, at any point during follow-up. Adrenal insufficiency screening tests (9am cortisol) will be conducted within the trial but confirmation of physician diagnosis of adrenal insufficiency, will be recorded, along with the relevant date and actions taken in response.

Deaths

Deaths from all causes over 18 months post randomisation. Date of death will be recorded, and time to death will be derived as days from randomisation to death.

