18.3 ANALYSIS OF SECONDARY OUTCOME MEASURES

PMR symptom severity measures, PMR activity score, and Patient-reported quality of life measures over 18 months: analysis of PMR-IS domain scores, health-related quality of life (EQ-5D-5L Utility), PMR-Activity Score will use multivariable repeated measures linear regression adjusting for minimisation factors, baseline value, treatment group, baseline-by-time interaction (if appropriate), age, time, and time-by-treatment group interaction. Centre will be fitted as a random effect, if feasible and has a positive variance component. Time will be fitted as a continuous variable, and the estimated time-by-treatment interaction effect with 95% CI and significance will be presented.

Time to steroid cessation, Time to PMR relapse: time to event will be calculated and summarised using Kaplan-Meier estimates. Adjusted hazard ratios will be estimated using Cox proportional hazards regression or parametric alternative, with covariates for minimisation factors (fitting centre as a random effect, if feasible) age and treatment group, and reported with 95% CI.

Steroid free remission at week 80 post randomisation will be summarised by treatment group and overall.

Number of relapses over time: A multivariable negative binomial regression model will be used to explore the number of relapses reported over follow-up time with an offset term for time at risk, adjusting for minimisation factors, age and treatment group. Centre random effects will be explored, assuming a Gamma distribution. Adjusted difference in rate of relapse with 95% CI will be reported.

Cumulative prednisolone-equivalent dose prescribed: A multivariable linear regression model will be fitted to log (cumulative glucocorticoid dose), adjusting for minimisation factors (fitting centre as a random effect, if feasible) age and treatment group. Adjusted mean fold difference in cumulative glucocorticoid dose with 95% CI will be reported.

Safety: The number of adverse events of special interest related to PMR or trial treatment, serious adverse events and SUSARs, in number of unique patients, will be reported by treatment received (MTX/LEF/Both/Neither) and by severity.

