Time to development of GCA will be summarised using Kaplan-Meier estimates. Adjusted hazard ratios will be estimated using Cox proportional hazards regression or parametric alternative, with covariates for minimisation factors (fitting centre as a random effect, if feasible) age and treatment group, and reported with 95% CI.

Adrenal insufficiency: The proportion of participants considered to be experiencing adrenal insufficiency will be reported in both groups.

Deaths: Number of deaths from all causes over 18 months post randomisation and time to death will be summarised by treatment received

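### Section 15.3 limits SAE reporting to events suspected related to PMR or a DMARD, contradicting 15.4, 15.4.1, 15.6 and the all-SAE outcome in 16.2.2; 18.3 names no SAE table by randomised arm

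*Protocol*

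**What the plan says.** Five parts of the protocol bear on this point.

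- **Which SAEs are reported.** Section 15.3: "in this study only serious adverse events that are suspected to be related to PMR or the IMPs will be reported". The reason given is that this population will have many events from other conditions and that DMARD safety is well known. Section 15.2 adds: "The IMPs are defined as the DMARDs, MTX or LEF".
- **The outcome.** Section 16.2.2, under Safety: "Serious adverse events (SAEs) and SUSARs regardless of relationship to PMR or investigational product reported over 18 months post randomisation".
- **Recording rules.** Section 15.4 has AEs and SAEs collected and reported from consent. Section 15.4.1 requires every SAE, SAR and SUSAR to be recorded and sent within 24 hours, with causality to trial drug or PMR as one of the recorded items. The Responsibilities part of 15.6 asks the investigator to report all SAEs and SARs. None of the three repeats the limit in 15.3. The period in 15.4 is to "continue until a minimum of 30 days post last dose of randomised treatment".
- **The objective.** Section 6.3: "to assess the impacts over 18 months of adding DMARD to steroids, by comparing treatment groups for". SAEs and SUSARs appear in the safety list that follows.
- **The planned tables.** Section 18.3: adverse events of special interest, SAEs and SUSARs "will be reported by treatment received (MTX/LEF/Both/Neither) and by severity". For deaths, the number and "time to death will be summarised by treatment received".

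**The concern.** The protocol gives sites two incompatible instructions on which SAEs to send. Under one of them, an outcome that the protocol itself names is never collected. An analysis plan cannot repair this, because it cannot analyse events that sites were told not to report. Sites in two countries feed one pooled analysis, so different sites could also resolve the conflict differently.

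The limit is also not neutral between arms. A DMARD-arm event can qualify through PMR or through a drug. A usual-care event normally qualifies only through PMR. The judgement is made with the allocation known, and section 15.2 itself concedes that causality is hard to assign because steroids cause many of the same events.

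The trial's rationale (section 5.4) is to weigh a small increase in DMARD harm against better disease control and less steroid toxicity. That needs a like-for-like count of serious events by randomised arm, and 18.3 does not name one.

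**Working it through.** The protocol gives no SAE rate, so there is no figure of its own to reproduce. The check is a comparison of the text, followed by illustrations on assumed inputs.

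**1. What is collected, under each reading**

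| If this governs | SAEs reported | Is the 16.2.2 outcome available? |
|---|---|---|
| 15.3 | Only those suspected related to PMR, MTX or LEF | No |
| 15.4, 15.4.1, 15.6 | All, with causality as a field | Yes |

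The protocol does not say which rule prevails.

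**2. What the limit could do to a comparison of arms**

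Let *p* be the true SAE risk, equal in both arms, and let *a* be the share of SAEs judged related (D for DMARD, U for usual care). For simplicity, assume at most one SAE per person.

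Recorded ratio = (*p* × *a*D) / (*p* × *a*U) = *a*D / *a*U. The base rate cancels.

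With an assumed *p* = 0.20 and assumed shares:

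| DMARD share | Usual-care share | Recorded risks | Ratio |
|---|---|---|---|
| 30% | 30% | 0.06 v 0.06 | 1.00 |
| 40% | 30% | 0.08 v 0.06 | 1.33 |
| 50% | 25% | 0.10 v 0.05 | 2.0 |
| 50% | 20% | 0.10 v 0.04 | 2.5 |
| 30% | 10% | 0.06 v 0.02 | 3.0 |
| 50% | 10% | 0.10 v 0.02 | 5.0 |

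Where the shares are equal at 30%, the ratio is unbiased, but 20 − 6 = 14 of every 20 SAEs are still lost.

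**3. What the planned tables compare**

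*Both* consists of people who moved from MTX to LEF because MTX was not tolerated or did not work (7.3.2, 13.1.14, 13.2). *Neither* combines usual care with anyone allocated a DMARD who never starts. Take 100 per arm (half of 200), a never-start share *f* and a usual-care crossover share *g*, both assumed. The size of *Neither* is 100(1 − *g*) + 100*f*.

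- *f* = 0.10, *g* = 0.10: 90 + 10 = 100 people, of whom 10 (10%) were randomised to DMARD.
- *f* = 0.20, *g* = 0.10: 90 + 20 = 110 people, of whom 20 (18%) were randomised to DMARD.

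**4. The collection period**

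The outcome covers 18 months, about 1.5 × 365.25 = 548 days. Week 80 is 80 × 7 = 560 days, so follow-up to week 80 covers it. The rule in 15.4 is anchored to the last dose of randomised treatment. For usual care that anchor is undefined. For someone who stops a DMARD early, the stated minimum alone does not reach 18 months.

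**The case against.** Much can be said for the protocol, and several stronger readings should be set aside.

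- **That SAEs cannot be compared between the arms.** A reader might infer this, but it follows only if 15.3 prevails. Sections 15.4, 15.4.1 and 15.6 contain no limit, and 15.4.1 already holds causality as a field. If they govern, the data exist and a by-arm table can be made.
- **That steroid harms are filtered out.** The documents do not support this. Infection, diabetes, hypertension and fracture are collected in both arms as glucocorticoid toxicity (14.6, 14.7, 16.2.2). Adrenal insufficiency is captured separately, and all deaths are recorded (14.11). The lead-in to 15.3 speaks of conditions other than PMR or its treatment, so some sites may treat steroid harms as reportable. What stands is that these items do not add up to all SAEs, and that the operative sentence names only PMR and the IMPs.
- **That collection stops early after a DMARD is stopped.** The 30 days are a minimum. AE and SAE review is scheduled in both arms to week 80 (14.2), and people who stop treatment stay in follow-up (13.4, Withdrawal of treatment). What stands is that the rule should be aligned with the outcome.
- **That the randomised comparison is abandoned throughout.** It is not. GCA is modelled by treatment group, adrenal insufficiency is reported in both groups, and the DMEC may see data by randomised group. A treatment-received safety table is a common convention, and the SAP could add a by-arm table. Section 18.3 nevertheless names treatment received alone for SAEs and deaths, and a closed DMEC session is not a final analysis.

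The 15.5 footnote that begins "The following events should also be regarded as SAEs in participants receiving" refers to abatacept, which is not a trial drug. That is a separate clerical correction with no bearing on this point.

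**Conclusion.** The point holds as a contradiction that needs correcting. Section 15.3 cannot stand beside 15.4, 15.4.1, 15.6 and the 16.2.2 outcome, and 18.3 names only post-randomisation groups for adverse events of special interest, SAEs and deaths. If 15.3 is followed, the all-SAE outcome is not collected, and what is collected passes through an open-label judgement with more routes to qualify in one arm.

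The size is unknown. The ratios shown (1.00 to 5.0) are ratios of assumed shares and should not be read as estimates. An upward distortion for the DMARD arm is the more plausible direction because that arm has the extra routes, but the documents do not fix it: a higher share attributed to PMR in usual care would push the ratio below 1. The make-up of *Neither* likewise rests on assumed never-start and crossover shares.

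The primary outcome and the sample size of 200 are not affected. The correction is time-critical because SAEs that were never reported may not be recoverable later.

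**What to change.** 1. **Section 15.3:** state that all SAEs are recorded in both arms. Keep relatedness to PMR, MTX or LEF as a recorded field that drives expedited reporting only, and make 15.4, 15.4.1 and 15.6 read the same way. The existing list in 15.3.1 of hospitalisations not classed as SAEs can stay.
2. **Section 15.4:** state that AE and SAE collection runs in both arms from consent to week 80, or to 30 days after the last DMARD dose if that is later. This matches the 18-month outcome and gives usual care a defined end.
3. **Section 18.3:** make the main AE, SAE and death tables by randomised arm. Keep the MTX/LEF/Both/Neither table as a supplement.

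The cost is a protocol amendment and some extra SAE forms across 200 participants. No new contacts are needed, since AEs and SAEs are already reviewed at every follow-up visit and call.

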12.2 Investigational Medicinal Product (IMP) Definition

Within the trial, the following are classed as IMPs:

- methotrexate
- leflunomide

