15.4.1 SAEs AND SARs

All SAEs, SARs and SUSARs must be recorded on the SAE eCRF (in the case of SAEs and SARs) or SUSAR eCRF as appropriate and sent by secure file transfer to the CTRU via secure file transfer **within 24 hours** of the research staff becoming aware of the event.

Assessment of causality and expectedness must be made by an authorised physician. If an authorised physician is unavailable, initial reports without causality and expectedness assessment should be submitted to CTRU but must be followed up by medical assessment as soon as possible thereafter.

The original SAE/SUSAR Report CRF(s) should be retained by site until the event has reached a final outcome and all queries have been resolved (as determined by CTRU). When requested, please return original (wet-ink) initial and follow-up reports to CTRU and retain copies at site.

Each SAE will be described by:

- full details in medical terms and case description
- event duration (start and end dates, if applicable)
- action taken
- outcome
- seriousness criteria
- causality (i.e. relatedness to trial drug or PMR) in the opinion of the investigator
- whether the event would be considered expected or unexpected

Changes in outcome, seriousness criteria, causality, or significant / medically relevant changes to the event (key data) should be sent by secure file transfer to CTRU within 24 hours of becoming aware. Other follow up information should be sent by secure file transfer to CTRU when the event has reached a final outcome, or when requested. Events will be followed up until the event has resolved or a final outcome has been reached.

[figure not shown]
Please ensure that each SAE/SAR/SUSAR event is reported separately and not combined on one form.

Investigators must report all SAEs to their host institution in line with their local arrangements.

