15.6 RESPONSIBILITIES

Principal Investigator (or delegate) at site:

- Checking for AEs/SAEs during telephone follow-up assessments
- Checking for AEs/SAEs when participants attend for treatment / follow up.
- Using medical judgement in assigning seriousness, causality and expectedness using the Reference Safety Information approved for the trial.
- To ensure all SAEs and SARs (including SUSARs) are recorded and reported to the CTRU within 24 hours of becoming aware of the event and to provide further follow up information as soon as available. Ensuring that SAEs and SARs (including SUSARs) are chased with CTRU if a record of receipt is not received within 2 working days of initial reporting.
- Ensuring that AEs and ARs are recorded and reported to the CTRU in line with the requirements of the protocol.

- Communication to the GP of any clinically relevant change in the participant's medical condition that might affect their ongoing care, including management of co-morbidities.

Chief Investigator (or nominated individual in CI's absence):

- Clinical oversight of the safety of trial participants, including an ongoing review of the risk / benefit.
- Using medical judgment in assigning seriousness, causality and expectedness of SAEs where it has not been possible to obtain local medical assessment.
- Immediate review of all SUSARs.
- Review of specific SAEs and SARs in accordance with the trial risk assessment and protocol as detailed in the Trial Monitoring Plan.
- Assigning Medical Dictionary for Regulatory Activities (MedDRA) or Body System coding to all SAEs and SARs.
- Preparing the clinical sections and final sign-off of the Development Safety Update Report (DSUR).

CTRU:

- Central data collection and verification of AEs, ARs, SAEs, SARs and SUSARs according to the trial protocol onto a MACRO database.
- Reporting safety information to the CI, delegate or independent clinical reviewer for the ongoing assessment of the risk / benefit according to the Trial Monitoring Plan.
- Reporting safety information to the independent oversight committees identified for the trial (Data Monitoring & Ethics Committee (DMEC) and / or Trial Steering Committee (TSC)) according to the Trial Monitoring Plan.
- Expedited reporting of SUSARs to the Competent Authority (MHRA in UK), main REC and Sponsor within required timelines.
- Notifying Investigators of SUSARs that occur within the trial.

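### Section 15.3 reports only SAEs suspected related to PMR or the DMARDs, but 16.2.2 defines the safety outcome as SAEs of any cause; if sites follow 15.3, that outcome will be incomplete

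*Protocol*

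**What the plan says.** Protocol 15.3 is the operational definition of SAEs and SARs. It notes that these patients will have "numerous adverse events related to co-morbidities other than PMR or its treatment" and cites the known safety profile of DMARDs. On that basis it states that "in this study only serious adverse events that are suspected to be related to PMR or the IMPs will be reported". Section 12.2 ("Within the trial, the following are classed as IMPs") lists methotrexate and leflunomide only.

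Other sections set a wider scope:

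- 16.2.2, Safety, defines the outcome as "Serious adverse events (SAEs) and SUSARs regardless of relationship to PMR or investigational product reported over 18 months post randomisation".
- 15.4: "AEs and SAEs will be collected on the relevant eCRF and reported to CTRU from the date of consent".
- 15.4.1: "All SAEs, SARs and SUSARs must be recorded on the SAE eCRF". Each report then describes "causality (i.e. relatedness to trial drug or PMR) in the opinion of the investigator".
- 15.6 Responsibilities, among the principal investigator's duties: "To ensure all SAEs and SARs (including SUSARs) are recorded and reported to the CTRU within 24 hours".

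Sections 14.6 and 14.7 ask for serious and non-serious event reporting at telephone calls and visits in both arms, and say that this includes glucocorticoid-toxicity events.

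**The concern.** The protocol gives sites two incompatible rules for the events that make up a secondary safety outcome. This is a rule about collection, so the analysis plan cannot repair it: an SAE that was never reported is not there to be analysed. If some sites follow 15.3 and others follow 15.4.1, the pooled count does not measure one defined quantity.

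The comparison between arms is also exposed. Section 5.4 says that the expected small increase in methotrexate adverse effects must be weighed against better disease control and less steroid toxicity. A filter that admits events by suspected link to PMR or a DMARD, without naming steroid, is poorly suited to that comparison. Relatedness is judged by investigators who know the allocation (7.1). The DMEC's search for safety patterns (15.6 Responsibilities) would rest on the same filtered data.

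**Working it through.** No figure in the protocol bears on this point, so the check compares the text.

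**1. Scope of SAEs, section by section**

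| Section | Role | Relatedness condition on SAEs |
|---|---|---|
| 6.3 | Objective | None; the condition is attached to adverse events of special interest |
| 15.3 | Operational definition | Suspected related to PMR or the IMPs |
| 15.4 | Collection | None |
| 15.4.1 | Form and 24-hour route | None; relatedness is described on each report |
| 15.6 Responsibilities | Investigator's duty | None |
| 16.2.2 | Outcome definition | Explicitly none |
| 18.3 | Analysis | None stated |

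Section 15.3 stands alone. In 15.4.1 relatedness describes an SAE already reported; it is not a test for entry.

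**2. Possible reconciliations**

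- *The 16.2.2 outcome counts only what was reported under 15.3.* Its explicit statement about relationship would then have no content.
- *15.3 governs only rapid reporting, while all SAEs go on the eCRF.* Section 15.3 does not say so. Section 15.4.1 applies the 24-hour limit to all SAEs, and regulatory expediting is handled separately, for SUSARs, in 15.4.2.
- *The word all in 15.4.1 and the investigator's duties means all within the 15.3 definition.* This is possible, and it would remove those two conflicts. It leaves 15.3 against 16.2.2.
- *15.3.1 supplies the exclusions.* It lists certain kinds of hospital treatment and does not mention relatedness.

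None of these reconciles 15.3 with 16.2.2.

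**3. What is lost if sites apply 15.3**

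- Fatal events: kept. All deaths go on their own eCRF and are assessed against the SAE criteria (14.11).
- Non-fatal SAEs suspected related to PMR, MTX or LEF: kept.
- Non-fatal SAEs attributed to steroid: unclear. The lead-in to 15.3 sets aside only co-morbidities outside PMR and its treatment, which suggests that they were meant to count, and 14.6 and 14.7 ask for such events. The operative clause and the 15.4.1 causality field do not name steroid.
- Non-fatal SAEs judged unrelated: not reported as SAEs. Some may surface elsewhere, for example as an infection needing antibiotics (15.2), but not in the SAE count.

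**4. Effect by arm**

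A participant who takes no DMARD can enter through suspected relation to PMR only. One taking a DMARD can enter through PMR or the DMARD. Section 18.3 tabulates by DMARD actually taken, so under 15.3 the column for those who took none would hold PMR-related SAEs only.

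Let R be the true ratio of the risk of at least one SAE (DMARD to usual care). Let a1 and a0 be the shares of participants with an SAE who have at least one that qualifies under 15.3, in the DMARD and usual-care arms. Then

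reported ratio = R × (a1 / a0).

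The reported ratio equals R only if a1 = a0, and 15.3 gives no reason for them to be equal. The protocol states none of R, a1 and a0, nor an overall SAE rate, so no numerical bias follows.

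**The case against.** The strongest reply is that 15.3 is a deliberate, risk-adapted rule for well-known drugs in an older population with much co-morbidity, and that later references to all SAEs should be read within it. That is a fair reading of 15.4.1 and the investigator's duties, so the conflict there is the softer one. It does not answer 16.2.2.

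A reader might also infer more than the documents support:

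- *The SAE outcome cannot be produced at all.* Too strong. Deaths are captured separately, and glucocorticoid toxicity and adrenal insufficiency are outcomes in their own right (16.2.2). The outcome would be incomplete.
- *Steroid-related SAEs have no way in.* Not established. Sections 14.6 and 14.7 ask for glucocorticoid-toxicity events, and 15.2 recognises that steroids can cause many of the listed events and that causality is hard to assign. The fault is that 15.3 and the causality field are silent on steroid.
- *SAE collection stops early for those who stop DMARD, because 15.4 sets a minimum of 30 days after the last dose.* Not on the whole text. The schedule in 14.2 has AE/SAE review through week 80, and participants withdrawn from treatment stay in follow-up (13.4 Withdrawal of Treatment, 14.12).
- *The filter biases the comparison against the DMARD arm, by a stated amount.* Unequal capture is possible. Its direction and size depend on how investigators attribute events, about which the protocol says nothing; any number would rest on invented inputs.

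**Conclusion.** The contradiction between 15.3 and 16.2.2 is real, and nothing in the protocol resolves it. If sites apply 15.3, the 16.2.2 outcome loses non-fatal SAEs judged unrelated, and these cannot be recovered at analysis. The consequence depends on which rule sites follow: a site that follows 15.4.1 literally loses nothing.

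The number of events at stake cannot be derived. The only indication is the protocol's own expectation that events from co-morbidity will be numerous, and that remark concerns adverse events generally. Unequal capture by arm is a weakness of the rule; a bias of known direction is not shown. The primary efficacy analysis is unaffected. This should be corrected while SAEs can still be captured.

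**What to change.** Rewrite 15.3 so that every SAE in both arms is recorded on the eCRF whatever its suspected cause, through the week 80 follow-up. Add steroid to the causality field in 15.4.1, so that the choices are trial drug, steroid or PMR.

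If a lighter burden is wanted, apply the relatedness condition to the 24-hour route only: SAEs suspected related to PMR, its treatment or the IMPs. Amend 15.4.1 and the investigator's duties in 15.6 to match, and say when the remaining SAEs are entered.

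Narrowing 16.2.2 to related SAEs would also remove the contradiction. It would leave the open-label filter in the between-arm comparison, so it is the poorer choice.

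The cost is wording in 15.3, with 15.4.1 and the investigator's duties changed if the 24-hour route is narrowed, one added causality option, and a note to sites. Measured against 15.4.1 as written, no extra SAE reports are required. Measured against 15.3, sites would enter additional unrelated SAEs, in a number the protocol does not allow one to estimate.
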